9.8.2 Laboratory Parameters

Clinical laboratory assessments for renal function test, creatine kinase, urinalysis, BNP, NT-pro BNP, cardiac troponin, CK-MB, Lipase and Amylase will be performed at the Screening, Baseline, Week 2, Week 8, Week 12, Week 16 and Week 24 visits. Laboratory assessments for hs-CRP, TSH, T3, T4 and TNF α will be performed at the Screening and Week 24 visits. All other laboratory assessments will be performed at

Document Title:	Statistical Analysis Plan		
Version Number:	Final 1.0	Date:	18Oct2024
Protocol Number:	SARO.17.009	Sponsor Name:	Zydus Therapeutics INC

Screening, Week 12 and Week 24 visits. Laboratory values will be presented using the International System of Units (SI units).

Observed and changes from baseline values will be summarized descriptively (n, mean, median, standard deviation, minimum, and maximum values) at each assessment. A summary table of the categorical grade shift changes using the normal ranges from baseline to last study visit will be provided based on safety population.

Additionally, A summary of frequency count and percentages for abnormal liver enzyme parameters at each visit as well as worst value across all visits up to EOT will be provided by treatment group for the following categories.

- ALT $\geq 3 \times$ ULN, $\geq 5 \times$ ULN and $\geq 10 \times$ ULN
- AST $\geq 3 \times$ ULN, $\geq 5 \times$ ULN and $\geq 10 \times$ ULN
- Total Bilirubin $> 2 \times$ ULN
- ALT $\geq 3 \times$ ULN and Total Bilirubin $\geq 2 \times$ ULN
- ALT $\geq 3 \times$ ULN and Total Bilirubin $\geq 1.5 \times$ ULN
- AST $\geq 3 \times$ ULN and Total Bilirubin $\geq 2 \times$ ULN
- AST $\geq 3 \times$ ULN and Total Bilirubin $\geq 1.5 \times$ ULN
- ALP $> 1.5 \times$ ULN

A summary of abnormal liver enzyme parameters for patients with elevated ALT or AST at baseline (elevated at baseline is defined as, baseline ALT or AST $\geq 1.5 \times$ ULN) at each visit as well as worst value across all visits up to EOT will be provided by treatment group using frequency count and percentage for the following categories.

- ALT $> 5 \times$ baseline value at post-baseline visits
- ALT $> 3 \times$ baseline value at post-baseline visits
- ALT $> 2 \times$ baseline value at post-baseline visits with either a concomitant Total Bilirubin increase $> 2 \times$ ULN or INR increase by > 0.2
- AST $> 5 \times$ baseline value at post-baseline visits
- AST $> 3 \times$ baseline value at post-baseline visits
- AST $> 2 \times$ baseline value at post-baseline visits with either a concomitant Total Bilirubin increase $> 2 \times$ ULN or INR increase by > 0.2

For summary purposes, laboratory values that are listed as above or below particular thresholds will be numerically listed as above or below that threshold, respectively, by the minimum measured amount for that parameter. For example, if a parameter is measured to two decimal places, and has a result of “ > 6 ” then, for summary purposes, the value of 6.01 will be used. Values with “ $<$ ” or “ $>$ ” will be classified as Low or High, respectively, unless such classifications aren’t applicable for that parameter, in which case they will be classified as Normal.

A by-participants data listing will be provided for safety population, which contains data information for each available laboratory parameter based on safety population.

Document Title:	Statistical Analysis Plan		
Version Number:	Final 1.0	Date:	18Oct2024
Protocol Number:	SARO.17.009	Sponsor Name:	Zydus Therapeutics INC

The plot of correlation between peak Total Bilirubin vs. ALT values will be generated. The horizontal and vertical lines will be as such, divide the graph into quadrants indicate Hy's law thresholds.

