4.4 PATIENT WITHDRAWAL

Patients may withdraw from the entire study at any time without penalty and for any reason without prejudice to her future medical care. Although a patient is not obliged to give her reason for withdrawing prematurely, the PI will make a reasonable effort to obtain the reason while fully respecting the patient's rights. If there is a medical reason for withdrawal, the patient will remain under the supervision of the PI for follow-up of AE(s) as detailed in Section 9.4.1.6. Every effort will be made to continue clinical and/or laboratory follow-up, as appropriate, in patients who wish to withdraw from the study drug (Investigational product or placebo) and reasonable efforts will be made to contact a patient who fails to attend any follow-up appointments, in order to ensure that she is in satisfactory health. A patient's withdrawal of consent and agreement to undergo a final examination will be documented on the electronic case report form (e-CRF).

As far as possible, all assessments scheduled for end-of-treatment must be performed on all patients who receive the study drug but do not complete the study according to protocol. In addition, if patient withdraws from the study, any data collected during the period of time will be maintained as part of the study data.

 Zydus Discovery DMCC	CLINICAL TRIAL PROTOCOL Saroglitazar Magnesium – Phase 2A SARO.17.009	Confidential Page 43 of 82
---	---	-------------------------------

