4.5 STOPPING CRITERIA FOR INDIVIDUAL PATIENTS

The following clinical events warrant discontinuation of study drug; however, the patient will continue to be followed for safety, hormonal profile, liver function tests and lipid levels until the event has resolved, i.e., clinical laboratory value(s) has/have returned to baseline or is/are no longer of clinical significance. Discontinuation of study drug will only occur if mandated by safety events as defined below:

Approved by: [name]	Protocol No. SARO.17.009 Version No.: 5.0
------------------------------------	--

 Zydus Discovery DMCC	CLINICAL TRIAL PROTOCOL Saroglitazar Magnesium – Phase 2A SARO.17.009	Confidential Page 44 of 82
--	---	-------------------------------

- Discontinue any patient with an adverse event of Common Terminology Criteria for Adverse Event (CTCAE) grade 3 or higher that is possible or probable drug related and discontinue any patient with an AE of CTCAE grade 4 or higher regardless of attribution to drug.
- Serious AE that may be related to the drug and warrant discontinuation as per discretion of the PI.
- In the opinion of the PI, continuation of study drug poses a health risk to the patient.
- Evidence of drug induced liver injury requiring study drug discontinuation as shown in the algorithm below.
- The second LFTs [AST, ALT, ALP, GGT, serum protein, albumin and total bilirubin (with conjugated bilirubin)] values during the Screening Phase (those obtained at Visit 2) will be considered as baseline for the safety assessment.
 - If patients with abnormal baseline liver indices develop elevations of AST or ALT greater than 2 times baseline or total bilirubin greater than 1.5 X baseline values (BL) while on study, testing should be repeated within 48-72 hours. If there are persistent elevations in ALT or AST greater than 2 X baseline or TB greater than 1.5 X baseline values, then close observation (see DILI Guidance for definition, testing and physical examination 2-3 times per week) should be initiated or drug should be discontinued.
 - A decision to discontinue or temporarily interrupt a study drug should be considered based on factors that include how much higher baseline ALT and AST were relative to the upper limit of normal (ULN) and how much the on study ALT and AST levels have increased relative to baseline, in addition to whether there is concomitant elevation of bilirubin or INR.

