8.4.3 Safety Analysis

All safety analysis will be carried out on the safety population. The frequency tabulations of abnormal clinical laboratory values for the parameter will be presented for each treatment group by visit. Summary statistics for clinical laboratory parameters, ECGs, physical examination and vital signs will be presented for each treatment by visit.

All AEs observed during the study period will be listed. Incidence of all AEs reported during the study will be summarized using the MedDRA (version 19 or higher) by treatment group, frequency, severity, seriousness, relationship to study drug and expectedness per System Organ Class and Preferred Term.

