9.4.1.6 Follow-up of Adverse Events

All AEs experienced by a patient, irrespective of the suspected causality, will be monitored until the AE has resolved, any abnormal laboratory values have returned to baseline or stabilized at a level acceptable to the Investigator and Medical Monitor, until there is a satisfactory explanation for the changes observed, until the patient is lost to follow-up or until the patient has died.

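### For non-liver laboratory tests, the SAP's only categorical summary is a shift from baseline to an undefined last visit, so on-treatment abnormalities that settle can be missed in it

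*SAP*

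**What the plan says.** SAP 9.8.2 plans these laboratory outputs by arm:

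- **All tests, continuous:** "Observed and changes from baseline values will be summarized descriptively (n, mean, median, standard deviation, minimum, and maximum values) at each assessment".
- **All tests, categorical:** "A summary table of the categorical grade shift changes using the normal ranges from baseline to last study visit will be provided". The SAP does not say which visit counts as last.
- **Liver tests only:** threshold tables for ALT, AST, total bilirubin and ALP, given "at each visit as well as worst value across all visits up to EOT will be provided by treatment group for the following categories". For women with raised ALT or AST at baseline there are further tables by multiples of baseline. Also: "The plot of correlation between peak Total Bilirubin vs. ALT values will be generated".
- **All tests:** a by-participant listing.

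Protocol 8.4.3 is broader and does not confine itself to liver tests: "The frequency tabulations of abnormal clinical laboratory values for the parameter will be presented for each treatment group by visit". The table of differences from the protocol in SAP section 10 does not mention laboratory tables.

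Protocol 4.5 sets laboratory thresholds for stopping study drug. It says a stopped woman is followed "until the event has resolved, i.e., clinical laboratory value(s) has/have returned to baseline or is/are no longer of clinical significance".

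**The concern.** A shift table that looks only at the two ends of follow-up cannot show what happened in between. The loss matters here for two reasons. First, the protocol's own laboratory stopping thresholds can be crossed at any on-treatment assessment. Second, women stopped for a laboratory value are followed towards recovery, so the end of their follow-up is when the value is least likely to be abnormal. A woman who stays on drug with a rise between Week 2 and Week 16 that settles by Week 24 is lost from the table in the same way.

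At stake is the between-arm categorical comparison for muscle, pancreatic, renal and blood-count safety. Recruitment closed at 60 with 1:1 allocation (SAP 8.5), about 30 women per arm, so each woman is 1/30, or about 3.3 percentage points. A few missed cases can change how that comparison reads.

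**Working it through.** The plan gives no figure to reproduce. The check is a comparison of sections, followed by an illustration under stated assumptions.

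**1. Coverage of the protocol 4.5 laboratory thresholds in SAP 9.8.2**

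| Stopping parameter | By-visit or worst-value abnormality table? | On-treatment assessments per SAP 9.8.2 |
|---|---|---|
| ALT, AST, total bilirubin | Yes | not needed here |
| INR | Only in combination with ALT or AST | not needed here |
| CK, amylase, lipase, eGFR | No | Weeks 2, 8, 12, 16, 24 (five) |
| Hemoglobin, hematocrit, platelets, white cells | No | Weeks 12, 24 (two, as part of all other laboratory assessments) |

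None of the eight non-liver parameters has a worst-value, any-time or by-visit abnormality table.

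**2. Can a stop disappear from the shift table?**

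Take lipase. A value above ULN at baseline is an exclusion (protocol 4.3), and a value above ULN on study is a stopping criterion (protocol 4.5). Lipase that has returned to baseline is therefore not High. There are two routes:

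- If the last visit falls after recovery, the table shows no upward shift and the event is missed.
- If the last visit is the early-termination assessment, the value may still be High and the event is counted. Protocol 4.4 makes this route possible for women who leave early: "As far as possible, all assessments scheduled for end-of-treatment must be performed on all patients who receive the study drug but do not complete".

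Which route applies depends on a term the SAP leaves undefined. The same reasoning holds for CK and amylase, which are also excluded above ULN at baseline.

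**3. How much an end-only table can lose**

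Assumptions, none taken from trial data: chance p of an out-of-range value at each visit is 0.025 or 0.05; k visits with latent-normal correlation ρ of 0 to 0.7; no treatment effect; all visits attended; the last visit is Week 24.

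- P(ever abnormal) = 1 − E[Φ((c − √ρ·Z)/√(1−ρ))^k], with c = Φ⁻¹(1−p) and Z standard normal. At ρ = 0 this is 1 − (1−p)^k.
- Share of ever-abnormal women not abnormal at the last visit = 1 − p / P(ever abnormal).

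| k | p | ρ | P(ever abnormal) | Share missed at last visit |
|---|---|---|---|---|
| 5 | 0.025 | 0 | 1 − 0.975^5 = 0.119 | 1 − 0.025/0.119 = 79% |
| 5 | 0.025 | 0.7 | 0.074 | 66% |
| 5 | 0.05 | 0 | 1 − 0.95^5 = 0.226 | 78% |
| 5 | 0.05 | 0.7 | 0.135 | 63% |
| 2 | 0.025 | 0 | 1 − 0.975^2 = 0.049 | 49% |
| 2 | 0.025 | 0.7 | 0.042 | 40% |
| 2 | 0.05 | 0 | 1 − 0.95^2 = 0.098 | 49% |
| 2 | 0.05 | 0.7 | 0.080 | 38% |

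For a five-visit test and 30 women per arm, this is 30 × 0.074 = 2.2 to 30 × 0.226 = 6.8 ever-abnormal women. The last-visit column would hold 30 × 0.025 = 0.75 to 30 × 0.05 = 1.5.

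**4. Protocol against SAP**

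Protocol 8.4.3 asks for by-visit frequencies of abnormal values for clinical laboratory tests generally. SAP 9.8.2 specifies them for liver parameters only. SAP section 10 lists five differences from the protocol, and this is not one of them.

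**The case against.** The strongest reply is that an abnormality serious enough to stop drug is caught elsewhere. Protocol 6.2.1 makes a result that leads to discontinuation a criterion for adverse event reporting and requires a justification if it is not reported. Protocol 9.4.2 gives laboratory abnormalities that warrant a section 4.5 stop as an example of serious events. SAP 9.8.1 tabulates serious events and events leading to permanent discontinuation by arm. Much of this stands: most laboratory stops should appear in those tables with a count per arm. It does not close the gap. Serious status is left to the investigator's judgment, and findings judged not clinically significant are kept off the adverse event page (protocol 9.4.1.1). The tables also group by preferred term rather than by laboratory threshold, and abnormalities that did not lead to a stop may never reach them.

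Minimum and maximum values at each assessment do show that an extreme value occurred, and the listings show whose it was. Neither says how many women in each arm were abnormal.

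A reader might infer three stronger claims. The documents support none of them.

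- *That the main laboratory harms are hidden.* Liver injury, which has the most detailed stopping algorithm, is well covered by the worst-value tables and the peak plot.
- *That every woman stopped for a laboratory value will appear as normal.* Follow-up in protocol 4.5 may end when the value is no longer clinically significant. Protocol 9.4.1.6 likewise accepts that "any abnormal laboratory values have returned to baseline or stabilized at a level acceptable to the Investigator and Medical Monitor". Neither requires a normal value, baseline itself need not be normal (hemoglobin is excluded only below 10 g/dL), and the last visit may precede recovery.
- *That the SAP has withdrawn the protocol's by-visit tables.* SAP section 10 says the analysis follows both documents and that the SAP prevails where they contradict. Silence is not clearly a contradiction, so the status of those tables is open rather than settled.

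**Conclusion.** The point holds for non-liver laboratory tests. Their only categorical summary in SAP 9.8.2 is a shift to an undefined last visit, and all eight non-liver stopping parameters are affected. Transient abnormalities, including some that led to a stop and then resolved, can be missed in that table. Separately, and without any assumption, the SAP restates the protocol 8.4.3 by-visit tables only for liver tests and does not disclose the difference.

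The 63-79% (five visits) and about 38-49% (two visits) describe chance out-of-range values under the assumptions above. They show how much an end-only table discards. They do not estimate missed toxicity or bias between arms. The remedy is a better specification that the SAP already uses for liver tests, so the change is worth making, though it concerns a descriptive safety section and not the primary result.

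**What to change.** In SAP 9.8.2:

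1. Add a normal-range shift table from baseline to the worst post-first-dose value for all laboratory tests, with high and low separate and both scheduled and unscheduled samples included.
2. Keep baseline-to-last as an extra column, and define the last study visit, including for women who stop early and for recovery samples.
3. Restate the protocol 8.4.3 by-visit tables of abnormal values for all laboratory tests. If any are to be dropped, list that in section 10 with a reason.
4. Count the women in each arm who meet each protocol 4.5 laboratory threshold at any post-dose assessment.

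The cost is SAP wording and one or two extra descriptive tables from data already collected, with no protocol amendment. Worst-value tables will also pick up chance excursions in both arms, so they should be read as a comparison between arms and not as toxicity rates.

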 - The criteria for discontinuing or temporarily interrupting study drug are as follows:
 - When the baseline values were ≥ 1.5 X ULN but < 5 X ULN, discontinue if ALT or AST increases to > 3 X baseline.
 - Discontinue if ALT or AST increase > 2 X baseline and the increase is accompanied by a concomitant TBL increase to > 2 X baseline or the INR concomitantly increases by > 0.2 .
 - Discontinue and evaluate any patient with elevations of ALT/AST if sign or symptoms of right upper quadrant pain, abdominal pain, anorexia, nausea, vomiting fever, eosinophilia and/or rash are present.
 - If a patient lives in a remote area, they can be tested locally and the results be communicated to the investigator site promptly.

 Zydus Discovery DMCC	CLINICAL TRIAL PROTOCOL Saroglitazar Magnesium – Phase 2A SARO.17.009	Confidential Page 45 of 82
---	---	-------------------------------

- Total CK > 5X ULN
- Amylase or lipase > ULN
- eGFR < 60 ml/min/1.73 m² and where the value is reconfirmed after 24 hours. Additionally, any subject who requires renal replacement therapy should also be discontinued from drug.
- Complete Blood Counts: Hemoglobin < 10 g/dL or HCT < 30%; platelets < 100,000/microL; WBC < 4 x 10⁹/L.

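### SAP 9.8.2 tabulates the combined liver criterion only for women with baseline ALT or AST ≥1.5×ULN, a limit that protocol 4.5 does not place on it, so some women who meet it fall in no category of either abnormal-liver-enzyme summary

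*SAP*

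**What the plan says.** **Protocol 4.5** lists its liver criteria for discontinuing or interrupting study drug as separate bullets. The isolated-rise bullet (ALT or AST above 3× baseline) opens with a baseline condition: "When the baseline values were ≥ 1.5 X ULN but < 5 X ULN". The next bullet is the combined criterion: "Discontinue if ALT or AST increase > 2 X baseline and the increase is accompanied by a concomitant TBL increase to > 2 X baseline". An INR increase above 0.2 is the alternative to the bilirubin rise. This bullet carries no baseline condition.

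**SAP 9.8.2** plans two summaries of abnormal liver enzymes, each by visit and as worst value up to end of treatment.

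- The first has no baseline restriction. It counts ALT and AST at 3, 5 and 10×ULN, total bilirubin above 2×ULN, ALP above 1.5×ULN, and combinations of bilirubin with ALT or AST ≥3×ULN. It has no INR row and no row in multiples of baseline.
- The second is "A summary of abnormal liver enzyme parameters for patients with elevated ALT or AST at baseline", and the SAP sets that elevation at ≥1.5×ULN. It holds the multiples of baseline, including the ALT and AST rows for more than 2× "baseline value at post-baseline visits with either a concomitant Total Bilirubin increase" above 2×ULN or an INR increase above 0.2.

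**SAP section 10**, which tabulates differences from the protocol, does not mention liver tables.

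**The concern.** The SAP applies the baseline limit of one protocol bullet to a neighbouring bullet that has none. The combined criterion pairs an enzyme rise with a sign of impaired liver function, so a reader of the safety tables would want a complete count of it by arm. As planned, the rows leave out women who can meet the criterion from a baseline below 1.5×ULN, and the denominator is not the set of women to whom the protocol bullet applies as written. Protocol 7.5 also counts women who developed withdrawal criteria but were not withdrawn as deviations. A count by arm over all treated women would show how often the criterion was met, whether or not drug was stopped.

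**Working it through.** The plan gives no figure of its own to reproduce. The check treats the protocol criterion and the SAP categories as logical rules and looks for profiles that meet the first and none of the second.

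**Notation.** b is baseline ALT and a is on-study ALT, both in multiples of ULN. The same reasoning holds for AST. One baseline value is used for both documents. To be outside the restricted summary, a woman must have both ALT and AST below 1.5×ULN at baseline. In the examples AST and ALP meet no category.

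**Rules.**

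- Protocol 4.5: a > 2b, and (bilirubin > 2× baseline or INR increase > 0.2).
- SAP unrestricted summary: a ≥ 3, or bilirubin > 2×ULN, or ALP > 1.5×ULN. The combination rows all need ALT or AST ≥ 3×ULN and add nobody.
- SAP restricted summary, combined row: b ≥ 1.5, a > 2b, and (bilirubin > 2×ULN or INR increase > 0.2).

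**Uncovered enzyme window.** For b < 1.5, the values 2b < a < 3 satisfy the protocol's enzyme part but no ALT row. The width is 3 − 2b.

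| b (×ULN) | window for a (×ULN) | width |
|---|---|---|
| 0.8 | 1.6 to 3.0 | 1.4 |
| 1.0 | 2.0 to 3.0 | 1.0 |
| 1.2 | 2.4 to 3.0 | 0.6 |
| 1.4 | 2.8 to 3.0 | 0.2 |
| 1.5 | none | 0 |

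**Profiles.** Bilirubin ULN is 1.3 mg/dL (protocol 4.3, exclusion 4e), so 2×ULN is 2.6 mg/dL.

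| Profile | Protocol criterion | SAP unrestricted | SAP restricted |
|---|---|---|---|
| ALT 1.2 → 2.6×ULN, INR +0.3, bilirubin normal | met (2.6 > 2.4) | none | none |
| ALT 1.2 → 2.6×ULN, bilirubin 0.5 → 1.1 mg/dL | met (1.1/0.5 = 2.2) | none (1.1/1.3 = 0.85×ULN) | none |
| ALT 0.9 → 2.0×ULN, INR +0.3 | met (2.0 > 1.8) | none | none |
| ALT 1.4 → 3.1×ULN, INR +0.3 | met (3.1 > 2.8) | ALT ≥3×ULN only | none |
| ALT 1.5 → 3.1×ULN, INR +0.3 | met (3.1 > 3.0) | ALT ≥3×ULN | combined row |
| ALT 1.6 → 3.3×ULN, bilirubin 0.5 → 1.1 mg/dL | met (3.3 > 3.2) | ALT ≥3×ULN only | none |

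The first three rows are the gap. The fourth is counted but not recognised as combined. The last lies inside the restricted summary and is still not in the combined row, because the SAP refers bilirubin to ULN and the protocol to baseline.

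**Can enrolled women have such baselines?** Entry requires ALT ≥38 U/L at Visit 1, and SAP 9.7.1.2 expects some women recruited before that criterion existed. The ALT ULN is not stated, so it is assumed here.

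| Assumed ULN (U/L) | 1.5×ULN (U/L) | 2 × 38 = 76 U/L, in ×ULN |
|---|---|---|
| 25 | 37.5 | 3.04 |
| 30 | 45 | 2.53 |
| 35 | 52.5 | 2.17 |
| 40 | 60 | 1.90 |
| 45 | 67.5 | 1.69 |
| 55 | 82.5 | 1.38 |

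From 30 U/L upward, some eligible ALT values lie below the cut. At 25 U/L none does, and only women enrolled with ALT below 38 could fall in the gap.

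**Share outside the restricted summary on ALT alone.** Assume lognormal ALT with distribution function F, truncated to the eligible 38–250 U/L: share = [F(1.5×ULN) − F(38)] / [F(250) − F(38)]. With medians of 45, 60 and 75, log-SD of 0.4 and 0.5, and ULN of 30 to 45, this runs from 0.06 to 0.77. At median 60 and ULN 35 to 45 it is 0.26 to 0.56, or about 16 to 34 of the 60 women at which recruitment closed. Women with AST ≥1.5×ULN would lower it; women enrolled with ALT below 38 would raise it. Every input is assumed, and the result counts women outside the summary, not events.

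**The case against.** **The SAP never says these rows count stopping events.** Protocol 8.4.3 promises frequency tables of abnormal laboratory values, not a tabulation of the 4.5 criteria, and the SAP introduces its liver categories as additional. This stands. A reader might infer that a promised analysis was narrowed, or that a stated rate of protocol liver events is biased downward. The documents support neither, because no such rate is claimed. The change is a cheap improvement to reporting.

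**A stopped woman would not vanish.** A reader might infer that she appears in no liver output at all. Protocol 6.2.1 makes a test result leading to discontinuation a criterion for adverse event reporting. Protocol 9.4.2 gives laboratory abnormalities that warrant stopping under 4.5 as examples of medically significant events, subject to the investigator's judgment. SAP 9.8.1 tabulates serious events and events leading to permanent discontinuation. She is also in the descriptive summaries, the normal-range shift table, the listing and the bilirubin–ALT plot. This stands too, but none of these outputs identifies the combined criterion: the shift table compares baseline with the last visit, and the plot shows neither INR nor multiples of baseline.

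**Part of the bilirubin limb is already covered.** Any woman with bilirubin above 2×ULN is counted in the unrestricted bilirubin row, whatever her baseline ALT, though not labelled as combined. This stands. What is missed altogether is the INR limb, and bilirubin above 2× baseline but not above 2×ULN.

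**The protocol criterion may not cover every woman.** The text before it concerns repeat testing and begins "If patients with abnormal baseline liver indices develop elevations of AST or ALT greater than 2 times baseline", and the nesting of bullets may have been lost in the PDF. If that phrase governs the combined bullet, women with normal baselines drop out. Abnormal baselines below 1.5×ULN would still be covered by the protocol and left out of the SAP rows, so the gap shrinks but does not close.

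**Conclusion.** The mismatch is real and follows from the wording of both documents. The combined criterion has no 1.5×ULN limit in protocol 4.5 and has one in SAP 9.8.2, and the unrestricted summary does not fill the gap. It matters for completeness of reporting by arm and does not show that liver events would go unreported.

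Its size cannot be stated. A reader might take the 6% to 77% range as the frequency of missed events. It is only an assumed share of women whose ALT lies below the cut; with no event rate in the documents, the number meeting the criterion could be very small or zero.

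The difference in bilirubin reference is a separate discrepancy that also affects these rows. No view is taken here on which threshold is clinically right; the passages must be reconciled.

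**What to change.** In SAP 9.8.2:

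1. Take the two combined rows (ALT and AST above 2× baseline with a concomitant bilirubin or INR increase) out of the summary restricted to baseline ≥1.5×ULN. Present them for the whole safety population by treatment group, with women who have a post-baseline value as denominator, optionally split at baseline 1.5×ULN.
2. Keep the baseline restriction only for the isolated-rise rows.
3. Reconcile the bilirubin reference in these rows with protocol 4.5 before describing them as aligned with it. Moving the rows closes the INR limb for baselines below 1.5×ULN; the bilirubin limb stays open while the two documents use different references.
4. Note the change in SAP section 10.

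The cost is SAP wording and one table shell, with no new data: INR, bilirubin and enzymes are already among the planned laboratory assessments. The downside is that a few more women may be counted as having a liver signal.

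### For parameters with a Low or High class, the SAP classes signed laboratory results without comparing them with the normal range, so in-range or unplaceable results can be tabulated as abnormal.

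*SAP*

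**What the plan says.** SAP section 9.8.2 handles a result reported as above or below a threshold in two steps.

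- **Number.** The result is moved past its threshold "by the minimum measured amount for that parameter". In the SAP's example, "if a parameter is measured to two decimal places" and the result is `>6`, then "the value of 6.01 will be used".
- **Category.** Results with `<` or `>` "will be classified as Low or High, respectively". There is one exception: if such a class does not apply to the parameter, "in which case they will be classified as Normal". The SAP does not list the parameters it has in mind.

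Earlier in the same section the SAP promises "A summary table of the categorical grade shift changes using the normal ranges from baseline to last study visit". Protocol section 8.4.3 has a related output: "The frequency tabulations of abnormal clinical laboratory values for the parameter will be presented" by treatment group and visit.

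**The concern.** A sign on a laboratory result says that the result passed the assay's reporting limit. It does not say that the result left the reference range. The SAP derives a number that could be tested against the range, then takes the category from the sign. The exception depends on the parameter, not on where the value lies. It protects a parameter with no Low or no High class, but not an individual result of a parameter that has that class.

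For such a result, the shift table cannot follow both the sign rule and the normal ranges, and the SAP does not say which governs. At stake are entries in descriptive safety tables. A result could be shown as abnormal when it is not known to be, or a shift could appear when one visit's result is signed and the other is a plain in-range number.

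**Working it through.** **1. The SAP's own figure.** Substituted value = threshold + 10^(−decimals) for `>`, and threshold − 10^(−decimals) for `<`. For `>6` at two decimals: 6 + 0.01 = 6.01, which matches the SAP. In the same way, `<0.2` at two decimals gives 0.2 − 0.01 = 0.19.

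**2. Three ways to class the result.**

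- *SAP rule:* `<` is Low and `>` is High, or Normal if the parameter has no such class.
- *Substituted value:* compare 6.01 or 0.19 with the lower limit (LLN) and upper limit (ULN).
- *All consistent values:* call the result Low or High only if every value it could represent is outside that limit, Normal only if every such value is within the limits, and otherwise indeterminate.

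**3. Inputs.** The only limit below taken from the documents is the total bilirubin ULN of 1.3 mg/dL (protocol section 4.3, exclusion criterion 4e). All other limits are assumptions, varied to show the range of outcomes. So is the reporting threshold of 0.2. The `>6` rows assume an LLN of 2.

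| Result | Assumed limit on that side | SAP rule | Substituted value | All consistent values |
|---|---|---|---|---|
| `>6` (6.01) | ULN 5 | High | High | High |
| `>6` | ULN 6 | High | High | High |
| `>6` | ULN 8 | High | Normal | Indeterminate |
| `>6` | ULN 10 | High | Normal | Indeterminate |
| `>6` | none | Normal (exception) | Normal | Normal |
| Bilirubin `<0.2` (0.19) | LLN 0.3 | Low | Low | Low |
| Bilirubin `<0.2` | LLN 0.2 | Low | Low | Low |
| Bilirubin `<0.2` | LLN 0.1 | Low | Normal | Indeterminate |
| Bilirubin `<0.2` | LLN recorded as 0 | Low or Normal, depending on how the exception is read | Normal | Normal |
| Bilirubin `<0.2` | none | Normal (exception) | Normal | Normal |

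**4. Where the rules part.** If the threshold is at or beyond the limit, or the parameter has no limit on that side, all three agree. They differ only when the parameter has the limit and the threshold lies inside it: `>x` with x below ULN, or `<x` with x above LLN. With ULN 8, `>6` could stand for 7 or for 20. With LLN 0.1, `<0.2` could stand for a value on either side of 0.1.

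**5. Effect on a shift.** Take bilirubin at `<0.2` at one visit and 0.3 at the other. With LLN 0.1, the SAP rule tabulates Low to Normal, although the first result cannot be placed. With an LLN of 0 treated as a real limit, the same entry appears although both results are in range.

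**6. Scale of one entry.** SAP section 7.3 closes recruitment at 60, and allocation is 1:1, so 60 / 2 = 30 per arm. If all are evaluable, one participant moves a cell by 1/30 = 3.3 percentage points. This is the size of a single entry, not an estimate of how many there would be.

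**The case against.** The strongest reply has four parts.

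- **The exception may cover the clearest error.** If the lower limit is 0, no non-negative result can be Low, so Low is arguably not applicable and the result is Normal. This stands as a reasonable reading. The SAP does not state it, so it should be written down.
- **Most of the remaining cases are unresolved, not false.** What lies in range is the substituted number, which is only a convention. This also stands. For the same reason, simply testing 6.01 or 0.19 against the range is not enough: it would exchange possible false abnormals for possible false normals. But it does not rescue the SAP rule, which reports an unresolved result as abnormal with no qualification.
- **A specific convention for signed results can sit beside a general rule about normal ranges.** That is so in principle. Here the specific rule never consults the range, and the SAP does not explain how the two fit together.
- **The reach is small.** Agreed. Section 9.8.2 does not tie the sign rule to the protocol's frequency tables, the rule is the same in both arms, and by-participant laboratory listings will be provided.

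A reader might go further and infer that the sign alone decides every signed result, that the tables will contain false abnormal values, or that a sizeable share of results for particular analytes is affected. The documents do not support this. The exception removes parameters without the class, and no reporting limits or full ranges are given from which a count, a percentage or a list of exposed analytes could be derived.

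**Conclusion.** Wrong as written, minor severity. For a parameter that has the relevant class and whose reporting limit lies inside the normal range, the SAP rule can tabulate as abnormal a result that is in range or cannot be placed. This does not fit a shift table said to use the normal ranges.

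The frequency cannot be calculated and may be low or nil; it depends on the central laboratory's reporting limits and ranges. The effect is confined to the descriptive shift table and possibly the abnormal-value frequencies in protocol section 8.4.3. Means use the substituted number and not the class. The efficacy analyses, the liver tables based on multiples of ULN or baseline, and the bilirubin-versus-ALT plot do not use the class either.

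**What to change.** In SAP section 9.8.2, replace the classification sentence with:

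> A signed result is classed by comparing its reporting threshold with the laboratory's lower and upper limits: Low or High only if every value consistent with the result lies outside that limit; Normal if every such value lies within the limits (including parameters with no limit, or a limit of 0, on that side); otherwise it is shown as indeterminate and not counted as a shift.

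The substitution rule can stay as it is for numeric summaries. The cost is one sentence, a comparison with laboratory limits that the shift table needs anyway, and one extra category in the affected tables. No new data are needed. If the SAP can no longer be amended, make the change as a deviation and record it with its reason in the clinical study report, as the SAP introduction provides.
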